- Uncontrolled Hyperthyroidism
- Congenital heart disease
- HCM, ARVC, channelopathies
- Contra-indications to AAD
- Long QT syndrome

- Received already adequately dosed all level 1 drugs (sotalol, propafenone, and flecainide) and >6 weeks amiodarone
- Pure (typical) atrial flutter as documented on one occasion

INVESTIGATION DESIGN

Type

Randomized study design. Experienced centres/operators with a load of > 50 cryoablations/year.

Randomization

1:1 at the time of inclusion

SAMPLE SIZE

The maximal expected 1 year success on AAD is 50% and minimal expected success of CBA is 72%. [3,14,15,20,21,22] With a power of 0.8 and a significance of 0,05, approximately 76 patients should be included in each arm. A total number of 167 patients need to be included in the study when anticipating that 10% of the patients will not be followed as required.

INTERVENTIONS

Run-in period (from month -1 till month 0)

Holter recording in the month after inclusion, preferably directly after inclusion to avoid extra visits.

MRI or CT scan to measure LA volume and PV sizes and anatomy is encouraged

(optional – if done it should be done in both branches)

Ablation arm (at month 0):

The ablation approach should be as standardised as possible, and will be discussed at the investigators meeting

After venous punctures, 5000 IE of heparin is administered and after the transseptal puncture (TSP) this is repeated. Hereafter, heparin infusion is started with a target ACT of at least 275-300 s. A multipolar catheter will be introduced into the coronary sinus. Single TSP will be performed (guided by X-ray and intracardiac echocardiography or transoesophageal echocardiography). The 12 Fr steerable sheath is introduced into the LA, and the second generation (large) cryoballoon with the Achieve catheter is introduced. Before ablation is started, the veins are checked for entrance and exit block. If there is conduction a balloon application is given during 300 s. The occlusion grade, maximal freezing temperature and time to isolation are noted. Every vein with potentials is ablated at least twice with at least one grade IV occlusion, except when PNP occurs at the right upper PV. If not isolated, a third application can be given. If after the third application the vein is still not occluded it is up to the physician to decide to do another balloon application or to use a freezer catheter.

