If isolated, the veins are checked after 30 minutes again for entrance and exit block. The left sided veins are ablated while pacing from the distal CS electrodes and when ablating the right sided veins the phrenic nerve is stimulated to prevent phrenic nerve palsy (PNP). When all veins are isolated AF induction is preformed, 5 s of pacing with CL 200 ms from the distal CS, LA roof (twice) en the HRA. Procedure times , X-ray times, and the radiation dose (mGy) are noted.

Ablation should be scheduled 4 weeks after cardioversion/inclusion. All patients should

be anticoagulated for at least 4 weeks prior to ablation. Antiarrhythmic drugs are maintained after cardioversion. One day before or the day of ablation a TEE will be made to exclude a LAA thrombus. Anticoagulation can be continued if this is the protocol of the participating centre, and the local protocol per ablation should be followed.

Proposed first level:

A: propafenone 300 mg BID / 150 mg QID if < 70 years and > 70 kg

propafenone 150 mg TID if ≥ 70 years or < 70 kg

B: sotalol 120 mg BID if men ≤ 70 years, cr ≤ 1,5mg/130 µmol, > 70kg;

80 mg TID if men ≥ 70 years, cr > 1,5mg/130 µmol, < 70kg;

if women ≤ 70 years; cr ≤ 1,2/110 µmol

80 mg once if women > 70 years or cr > 1,2 mg/110 µmol

C: Flecainide : Apocard Retard 100 mg/day as startdosis 4 to 5 days

Further 200 mg/day

Tambocor 100 mg BID if preferred

Proposed second level:

Amiodarone: loading 14 days with 600 mg/day

One week 400 mg/day

Maintenance 200 mg/day

Drug arm:

Anticoagulation should be continued per protocol (4 weeks) after the cardioversion. If the CHADS2VASC is \leq 2, anticoagulation is left at the discretion of the physician. A first level antiarrhythmic drug regimen is started at the month -1, time of the inclusion and

an adequate dosage is prescribed. If the patients' condition requires so, a reduced dosage can be used during the first (5-7) days.

If at month 0, at the first clinical visit, the drug therapy does not look sufficient, another

Level 1 treatment can be used. This can be repeated if the clinical condition requests so.

The second slevel antiarrhythmic drug therapy is only allowed after failure of at least one level 1 drug. As this is amiodarone, its final efficacy can only be judged 6 months after its initiation.

FOLLOW UP : see flow charts Is in agreement with proposal in ref 23.

- 24 hour Holter:

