 - after inclusion (month -1) and repeated at months 3 .This will be done with the study Holter without necessarily influencing the therapy (so called blanking period)
- 48 hour Holter: with a clinical device
 - at the end of 6 months .
- 7 days Holter: with a clinical device
 - at the end of 12 months .
- Clinical visits :

should be performed by the study nurses/supervised by the investigators

- At months 3, 6, and 12 months after ablation
- Additionally at month 0 for the drug arm, while the ablation group is admitted
- Office ECG ;
 - ° at month 3, 6 and 12
- Drug management:
 - AAD: After 3 months stop AAD in the ablation arm in those patients free of AF episodes.
 - OAC: After 6 months consider stopping oral anticoagulation, or replacing them with antithrombotic medication in patients free of AF episodes if the scores allow so.
- Echocardiogram:
 - At month 12 a new echocardiogram is obtained to assess the LA volume and diameter.
- QOL with disease specific questionnaire (AFQOL 18)
 - At baseline and at month 12
- Blood samples
 - At baseline and at months 6 and 12
 - Thyroid tests (TSH), liver function (AP, SGOT, SGPT), creatinine

- Drug diary
 - At baseline, at month 0 and at months 6 and 12 for all patients in both arms
- Cost calculation: data should be prospectively collected in CRF at the time of scheduled and unscheduled visits, based on costs as foreseen in the reimbursement of the RIZIV/INAMI and additional drug costs.

CROSS OVER

Is allowed after 6 months. This implies that at 12 months we will be able to do not only ITT but also OTA.

SERIOUS ADVERSE EVENTS

SAE's are expected to happen in 7% in the ablation arm, and at a rate of 12-15% in the drug arm, because of side effects and 3% because of proarrhythmia (20).

ENDPOINTS

Primary endpoints

- Sinus rhythm at clinical visit at 1 year after the ablation, or with AAD
- Freedom of AF with all measurements

Secondary endpoints

- Reduction of LA volume in successfully treated patients
- Number of cardioversions
- Percentage of patients on AAD after 6 and 12 months

- Vascular complications
- Stroke, TIA
- SAE in both groups
- Number of cross-overs (with OTA)

[figure not shown]

Figure 1. AAD : antiarrhythmic drugs; LA: left atrial; QOL: quality of life; R: randomization

STUDY ORGANISATION

Steering committee : [name], [name], [name], [name]

DMSB : [name], [name], [name]

One central study coordinator (University Hospital Ghent) – [name]

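### The two-application minimum is waived for phrenic nerve palsy only at the right upper vein, although the nerve is stimulated at all right-sided veins to prevent it

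*Protocol*

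**What the plan says.** All the procedural text is in Protocol, INTERVENTIONS, Ablation arm (at month 0).

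- **Minimum and exception:** "Every vein with potentials is ablated at least twice with at least one grade IV occlusion, except when PNP occurs at the right upper PV".
- **Phrenic monitoring:** "when ablating the right sided veins the phrenic nerve is stimulated to prevent phrenic nerve palsy (PNP".
- **Status of the instructions:** "The ablation approach should be as standardised as possible, and will be discussed at the investigators meeting".

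INVESTIGATION DESIGN, Type restricts who may take part: "Experienced centres/operators with a load of > 50 cryoablations/year".

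Three of the secondary endpoints under ENDPOINTS concern harm: "Vascular complications", stroke or TIA, and "SAE in both groups". PNP is not named there. BACKGROUND describes phrenic nerve paresis as the one side effect specific to cryoballoon ablation (CBA).

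**The concern.** The exception is narrower than the risk that the protocol itself recognises. If palsy appears during the first application at a right-sided vein other than the upper one, the minimum still calls for a second. An operator who rightly stops then departs from the written rule, and one who follows it to the letter freezes again beside an injured nerve. For patient safety the rule should match what a careful operator would do.

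A softer point goes with it. PNP is neither a vascular complication nor a stroke or TIA, so the listed endpoints count it only when it is a serious adverse event (SAE). RATIONALE mentions safety as well as efficacy when it introduces the comparison with medication, and remarks that earlier trials paid too little attention to the side effects of ablation. A descriptive account of the device-specific harm would fit that intention.

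**Working it through.** **1. The two instructions side by side**

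| Question | Right upper vein | Other right-sided veins |
|---|---|---|
| Phrenic nerve stimulated to prevent PNP? | Yes | Yes |
| At least two applications if the vein has potentials? | Yes | Yes |
| Minimum waived if PNP occurs? | Yes | No waiver written |

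The monitoring instruction speaks of right-sided veins in the plural. The exception names one vein.

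**2. Is the minimum discretionary?** The sentence states it as what is done for every vein with potentials. The next sentences use different language: a third application is something that can be given, and what follows is left to the physician. So the section marks discretion where it intends it, and the two-application minimum is not marked that way. Each application is set at 300 s, and the section contains no instruction to end one early for palsy.

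**3. Does any other text supply the waiver?** The section refers to following the local protocol, but that clause ends a sentence about continuing anticoagulation. It is not a clear waiver of the application rule.

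**4. Does it reach the analysis?** CROSS OVER mentions intention-to-treat analysis and a second analysis, abbreviated OTA. No available text excludes or reclassifies a patient for receiving one application instead of two.

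**5. The plan's own figure, and what a named PNP outcome could show.** Inputs from SAMPLE SIZE: success 0.50 against 0.72, significance 0.05 (taken as two-sided), power 0.80. With pooled variance and no continuity correction, and mean proportion 0.61:

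- n per arm = [1.960 × √(2 × 0.61 × 0.39) + 0.842 × √(0.50 × 0.50 + 0.72 × 0.28)]² / 0.22² = 76.0, which matches the stated 76.
- Total: 152 × 1.10 = 167.2, in line with the stated plan that "A total number of 167 patients need to be included in the study". Dividing by 0.90 instead gives 168.9, that is 169.

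Nothing in these figures depends on PNP. For the precision of a descriptive PNP outcome, 1:1 allocation gives 167 / 2 = 83.5, taken as 83 ablated patients if all assigned patients are ablated (cross-overs would add to this):

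- One patient is 1/83 = 1.2 percentage points.
- With 0 cases in 83, the exact two-sided 95% upper limit is 1 − 0.025^(1/83) = 4.3%. With 84 patients it is also 4.3%, and with 76 it is 4.7%.

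These limits would apply to any event observed in none of 83 patients. They are not an estimate of the PNP rate. The documents give no such rate, no split by vein and no share that is serious.

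**The case against.** The strongest reply is that this makes a mandate out of a summary sentence. The protocol wants the approach standardised as far as possible but defers discussion to the investigators meeting. It admits only centres or operators with more than 50 cryoablations a year. It stimulates the nerve in order to prevent palsy, which works only if the operator acts on what the stimulation shows. Nothing tells anyone to carry on after palsy. Much of this stands: operators would probably stop, and the meeting may close the gap. It does not change what the written rule says, and a written rule is the natural tool for standardisation.

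Four stronger readings are tempting, and the documents do not support them.

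- *Patients will be refrozen after palsy.* This needs a strictly literal reading by experienced operators, and no frequency can be given.
- *PNP will go unreported.* The SAE definition, the case report form (CRF), the flow charts, the SAP content and part of the protocol were not available. The expected 7% SAE rate in the ablation arm is not broken down and could include PNP.
- *The arms are treated unequally on safety.* Non-serious drug side effects are not listed as endpoints either.
- *A stated safety hypothesis is left untested.* The safety comparison appears in RATIONALE. HYPOTHESIS covers sinus rhythm, quality of life and left atrial volume only.

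**Conclusion.** The point holds as a defect in a written rule: the exception covers one right-sided vein, while the protocol guards the nerve at all of them. It matters for patient safety and costs almost nothing to correct. Its practical effect is probably small, on the assumption that experienced operators stop for palsy wherever it occurs. The number of patients affected cannot be estimated from the documents. Primary endpoints, sample size and power are unaffected.

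The endpoint part is weaker. The list reaches PNP only through SAEs, but that is not a shown omission, because PNP may be captured in material not seen here. It is a low-cost descriptive addition.

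**What to change.** **Procedure.** Replace the exception with: *except when PNP occurs during ablation of any right-sided vein, in which case the application is stopped at once and the two-application minimum is waived for that vein and for any remaining right-sided vein unless phrenic function has recovered.* Waiving the minimum only at the affected vein would not be enough, because two applications would still be required at a neighbouring right-sided vein beside an injured nerve.

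**Reporting.** Unless the CRF already does so, record PNP for every ablated patient, including cross-overs: the vein, status at the end of the procedure, any palsy first recognised later, and resolution as known at the existing visits ("At months 3, 6, and 12 months after ablation"). Where resolution cannot be established, record it as not known. Cross-over is allowed only after 6 months, so those patients would be asked at whichever scheduled visits remain, possibly month 12 only. Report PNP descriptively, and keep non-serious cases out of the between-arm SAE comparison.

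**Cost.** One changed clause, one procedure-form item and one short question to ablated patients at existing visits. To catch palsy recognised late, the question cannot be limited to patients with palsy at the end of the procedure. No new visit or test is needed.

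**Downsides.** A few right-sided veins will receive fewer than two applications. Without a diaphragm test, silent persistent palsy can be missed.

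### No printed sotalol line gives a man with raised creatinine less than 240 mg/day, although the same list lowers the dose for women on creatinine alone

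*Protocol*

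**What the plan says.** The doses are in the Protocol under INTERVENTIONS, in the list headed Proposed first level, item B.

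- Men, standard line: "sotalol 120 mg BID if men ≤ 70 years", with creatinine up to 1.5 mg and weight above 70 kg as further conditions.
- Men, flagged line: "80 mg TID if men ≥ 70 years, cr > 1,5mg/130", followed by weight below 70 kg. Commas separate the three conditions; neither *and* nor *or* is printed.
- Women, standard line: "if women ≤ 70 years; cr ≤ 1,2/110". It has no dose of its own and follows directly on the 80 mg three-times-daily entry.
- Women, flagged line: "80 mg once if women > 70 years or cr > 1,2 mg/110". Here *or* is printed, so creatinine alone is enough.

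The Drug arm paragraph sets the timing: "A first level antiarrhythmic drug regimen is started at the month -1". It adds that "an adequate dosage is prescribed", and that, if the patient's condition requires it, "a reduced dosage can be used during the first (5-7) days".

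**The concern.** Among the level 1 drugs, creatinine appears only in the sotalol lines, so the protocol itself makes it a sotalol dosing criterion. A reader would expect a line triggered by raised creatinine to lower the amount of drug given per day. The women's flagged line comes to 80 mg/day. The men's flagged line changes the size and number of doses but not the daily total.

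What is at stake is the safety of drug-arm men who are given sotalol from this list. A prescriber who follows it for a man with raised creatinine finds either an unreduced daily dose or no applicable line.

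**Working it through.** **Inputs.** All doses are from Protocol, Proposed first level, items A and B. The protocol gives single doses and frequencies, so daily totals are single dose × doses per day.

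| Line | Calculation | mg/day |
|---|---|---|
| Sotalol, men, standard | 120 × 2 | 240 |
| Sotalol, men, flagged | 80 × 3 | 240 |
| Sotalol, women, flagged | 80 × 1 | 80 |
| Sotalol, women, standard (if it shares the 80 mg three-times-daily entry) | 80 × 3 | 240 |

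**Step 1. Change for men.** Daily total: 240 − 240 = 0 mg. Average dosing rate: 120/12 h = 10 mg/h and 80/8 h = 10 mg/h. Only the single dose falls: (120 − 80)/120 = 33%.

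**Step 2. Does the reading of the commas matter?** Take a man whose only flag is creatinine above 1.5 mg.
- *Or*: he meets the flagged line and gets 240 mg/day.
- *And*: he fails the standard line on creatinine and the flagged line on age and weight, so no line covers him. A man with all three flags gets 240 mg/day.

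Neither reading produces a total below 240 mg/day.

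**Step 3. Comparison with women.** A woman with creatinine above 1.5 mg is also above 1.2 mg and gets 80 mg/day. Under the *or* reading for men, the ratio at the same creatinine is 240/80 = 3. This uses only printed doses. A fall within women of (240 − 80)/240 = 67% can be stated only if the standard line does share the entry above it.

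**Step 4. Could splitting the dose serve as the reduction?** The documents give no half-life, so this is an illustration: one compartment, immediate absorption, half-life h assumed between 6 and 48 h. Steady-state peak, in mg, = D/(1 − 2^(−τ/h)), with D the single dose and τ the interval in hours.

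| h (hours) | 120 mg, τ = 12 | 80 mg, τ = 8 | Change | 80 mg, τ = 12 | Change |
|---|---|---|---|---|---|
| 6 | 160.0 | 132.6 | −17.1% | 106.7 | −33.3% |
| 12 | 240.0 | 216.2 | −9.9% | 160.0 | −33.3% |
| 24 | 409.7 | 387.8 | −5.4% | 273.1 | −33.3% |
| 48 | 754.2 | 733.3 | −2.8% | 502.8 | −33.3% |

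Splitting lowers the peak by 3% to 17%, and by less as the half-life lengthens. It leaves the average level unchanged.

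**Step 5. Does anything elsewhere supply the reduction?** The allowance for a lower dose covers the first 5 to 7 days and is not tied to creatinine. The month 0 change of level 1 drug is triggered by insufficient effect. The inclusion and exclusion criteria name no renal limit. Creatinine is measured at baseline and at months 6 and 12, but no dosing action is attached to the result.

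**The case against.** The strongest reply is that the list does not bind anyone. Its doses are headed as proposed, the prescriber is told to give an adequate dose, and patients need to be suitable for only one of the first-step drugs, and/or for amiodarone. Contra-indications to antiarrhythmic drugs and long QT syndrome are exclusions, and creatinine is known at baseline. All of this stands, and it lowers the severity. None of it states a lower sotalol dose for a man with raised creatinine.

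Secondly, the commas are ambiguous. The women's flagged line prints *or*, but the men's flagged line mirrors the men's standard line, where the commas most naturally mean *and*. A reader might infer that every man with raised creatinine is definitely assigned an unreduced dose. The text does not settle that: on the *and* reading he has no line at all. The defect is then a gap, which still needs closing.

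Thirdly, the inconsistency does not show which entry is wrong. A smaller, more frequent dose for men could be deliberate, and 80 mg once daily for women could be the odd entry. This also stands: the documents do not show the intended dose.

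Fourthly, two supporting comparisons are weak. The women's standard 240 mg/day is inferred from layout. The propafenone list does reduce the total on its flagged line ("propafenone 150 mg TID if ≥ 70 years or < 70 kg", so 600 to 450 mg/day, 25%), but on age and weight only, and says nothing about a renal step. The conclusion should rest on neither.

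**Conclusion.** The point holds in limited form. Both men's sotalol lines total 240 mg/day, so creatinine above 1.5 mg never leads to a lower printed daily dose for a man: the change is 0% on the *or* reading, and there is no line for raised creatinine alone on the *and* reading. For women, the list explicitly gives 80 mg/day on creatinine alone. This part needs only the printed doses; the peak-level figures are an illustration under assumed half-lives.

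A reader might go further and infer that 240 mg/day is an overdose in these men, or that the trial's adverse-event rates, power or endpoints are compromised. The documents do not support that. They give no benchmark for an excessive dose and do not say how many men with raised creatinine would receive sotalol. It is a minor to moderate patient-safety correction to a proposed dosing list, held with moderate confidence.

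**What to change.** Amend item B of the Proposed first level list in one edit:

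1. Print *or* between the conditions of the men's flagged line, so that raised creatinine alone has a line.
2. At least for creatinine above 1.5 mg, set a daily total below 240 mg. One example is 80 mg twice daily: 80 × 2 = 160 mg/day, a reduction of (240 − 160)/240 = 33%. The clinical lead should set the final dose.
3. Give the women's standard line its own printed dose, because it now appears to share the 80 mg three-times-daily entry.

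The cost is a short protocol amendment, with no change to visits, endpoints or sample size. The downside is possibly slightly lower sotalol efficacy in a small subgroup. As an assumption only: if 2 to 10 of the 76 drug-arm patients were affected and each lost 10 percentage points of success, arm success would fall by 2 × 10/76 = 0.3 to 10 × 10/76 = 1.3 points, against a planned difference of 72 − 50 = 22 points.

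### The visits and first primary endpoint are timed from ablation, a post-randomisation event in one arm, so late- or never-ablated patients and the drug-arm year lack a fixed endpoint date

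*Protocol*

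**What the plan says.** Under Randomization, allocation is "1:1 at the time of inclusion". Under Interventions there is a run-in from month -1 to month 0, with no arm named, and ablation is placed at month 0. The ablation text adds: "Ablation should be scheduled 4 weeks after cardioversion/inclusion". In the drug arm, "A first level antiarrhythmic drug regimen is started at the month -1", which is the time of inclusion.

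Under Follow up, the clinical visits are set "At months 3, 6, and 12 months after ablation". The next line gives the drug arm an extra visit at month 0, to coincide with the ablation arm's admission. Holter, ECG, echocardiogram and quality of life are listed by month number without mention of ablation. The drug diary is due at baseline and months 0, 6 and 12 in every patient of either arm.

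Under Endpoints, the first primary endpoint is "Sinus rhythm at clinical visit at 1 year after the ablation, or with AAD". The Cross over section says that both an ITT and an OTA analysis will be possible at 12 months.

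The text available gives no visit windows, no maximum delay to ablation, and no rule for a patient randomised to ablation but not ablated.

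**The concern.** An ITT comparison needs an outcome for every randomised patient at a time that does not depend on what happened after randomisation. Here the visit line and the first primary endpoint depend on the date of a procedure that only one arm receives.

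The protocol's own conditions allow that date to move. Ablation is counted from cardioversion or inclusion, which need not coincide. At least four weeks of anticoagulation must come first, and a transoesophageal echocardiogram must exclude thrombus on the day or the day before. Some patients may therefore be ablated late or not at all.

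For the drug arm, the endpoint wording gives no start for the year. Sites could count it from drug start or from month 0. At stake are comparable endpoint timing in the two arms and a complete ITT set for a primary endpoint.

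**Working it through.** **The plan's own figure.** Inputs from Sample size: success 50% on drugs and 72% after cryoballoon ablation, power 0.80, significance 0.05 (taken as two-sided). The mean proportion is 0.61.

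n per arm = [1.96 × √(2 × 0.61 × 0.39) + 0.8416 × √(0.50 × 0.50 + 0.72 × 0.28)]² / 0.22² = (1.352 + 0.566)² / 0.0484 ≈ 76.

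This matches the stated 76 per arm, and 152 × 1.10 = 167.2 matches the stated total of 167. Nothing below changes the sample size; the 50% and 72% are reused.

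**Calendar on the planned schedule.** Randomisation and drug start are at month -1; ablation is at month 0.

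- Randomisation to month 12: 12 − (−1) = 13 months in both arms. Difference between arms: 0.
- Treatment start to month 12: 13 months on drug, 12 months after ablation. Difference: 1 month.

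**Ablation delayed by d months, with visits following it as worded.**

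- Time from randomisation: 13 + d for that patient, against 13 in the drug arm.
- Time from treatment start: still 12 against 13, so this gap does not grow with d.

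**Drug year counted from month -1.** The drug arm's endpoint falls at −1 + 12 = month 11. That is 12 months from randomisation, against 13 in the ablation arm.

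**Patient never ablated.** One year after ablation has no date, so the literal endpoint is undefined.

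**Size if never-ablated patients are dropped.** Assumptions: a fraction f of the ablation arm is never ablated; 50% of these succeed; 72% applies to those ablated. The documents give neither f nor the success rate of these patients. With about 84 patients in the arm (167 / 2 = 83.5), f of 5-10% is about 4 to 8 patients.

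- f = 5%: ITT success = 0.95 × 0.72 + 0.05 × 0.50 = 0.709. Overstatement: 72.0 − 70.9 = 1.1 points.
- f = 10%: ITT success = 0.90 × 0.72 + 0.10 × 0.50 = 0.698. Overstatement: 72.0 − 69.8 = 2.2 points.

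The difference from the drug arm would be 20.9 or 19.8 points instead of the planned 22.

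**Size of a one-month offset, as illustration only.** Assume a constant failure hazard with 50% success at 12 months. At 13 months success is 0.50^(13/12) = 0.472, which is 2.8 points lower. If the arms were truly equal and one whole arm of 76 were assessed a month later, the two-sided rejection rate would be about 6.4% instead of 5%. The documents give no time-to-failure curve, and sinus rhythm at a single visit need not behave this way.

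**The case against.** The strongest reply is that the protocol already has a common clock. The run-in is written without reference to arm, the drug arm has its own month 0 visit matched to the ablation admission, most assessments are listed by month number, and the diary schedule covers everyone. On that reading, timing from ablation is loose wording for month 12, and month 0 is already inclusion plus about four weeks.

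Much of this stands, and it rules out several stronger readings that a reader might infer:

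- *That one year differs between the arms by design, or that drug-arm patients have no endpoint visit.* On schedule, time from randomisation is equal, and the drug arm has a month 12.
- *That the one-month difference in time since treatment start is itself a bias.* ITT compares time since randomisation. The month before ablation is also not clearly untreated, because antiarrhythmic drugs are maintained after cardioversion.
- *That timing from ablation favours ablation.* Late ablation, or a drug year counted from month -1, would have the ablation arm assessed later from randomisation. For a cumulative endpoint this would tend to count against ablation; for rhythm at one visit the direction is unclear. Only the dropping of never-ablated patients supports a bias towards ablation, and no text says that they will be dropped.

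The Follow up section also points to flow charts. These, the SAP text and part of the protocol were not available, and they may define the anchor.

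What the reply does not remove is that the first primary endpoint and the visit line name ablation, not month 12. When ablation is late or does not happen, the two clocks disagree, and the available text does not say which governs.

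**Conclusion.** The point holds as a defect in how the endpoint time is defined. It does not show a difference built into the planned schedule.

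The wording leaves three cases open: patients ablated late, patients never ablated, and the start of the drug-arm year. The second bears most directly on ITT. Its effect is about 1.1 to 2.2 points in favour of ablation, only if such patients are dropped and only under the assumed 5-10% never ablated with 50% success. That is small against the planned 22 points. The third could move the drug-arm endpoint by one month. For late ablation, neither size nor direction can be given from the documents.

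The change is worth making because it is cheap and concerns a primary endpoint. Confidence is medium, given the material that could not be checked.

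**What to change.** - Define month 0 for every randomised patient as the randomisation date plus 4 weeks, whether or not ablation has been done. This sets assessment times only, not when anyone is treated.
- Reword the clinical visits as months 3, 6 and 12 on that grid in both arms, with visit windows.
- Reword the first primary endpoint as sinus rhythm at the month 12 visit on the same grid in both arms. This also settles the start of the drug-arm year.
- State that late-ablated and never-ablated patients are included in the ablation arm at that time point for ITT.
- Bring the flow chart and the SAP into line if they use another origin.

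The cost is wording; the sample size does not change. The downside is that a patient ablated d months late has 12 − d months after the procedure at the endpoint. A supportive analysis timed from ablation can be kept for readers who want the full post-procedure year, labelled as not being the ITT comparison.
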